## **General Information/ Background**

General anesthesia is a complex physiological state characterized by reversible loss of consciousness, whole-body analgesia, amnesia, and muscle relaxation. The term low-flow anesthesia describes inhalation anesthesia techniques that are administered with a semi-closed rebreathing system and have a rebreathing rate of at least 50%. The high standard of anesthesia machines, the existence of monitors that analyze the anesthetic gas composition continuously and in detail, and the increased knowledge about the pharmacodynamics and pharmacokinetics of inhalation anesthetics have greatly facilitated the safe administration of low-flow anesthesia. The terminology associated with low-flow anesthetic techniques may be based on rebreathing or fresh gas flow rates. The fresh gas flow rate is the most critical factor determining the rebreathing rate. Most patients can have low-flow anesthesia when modern re-breathing systems are used; the fresh gas flow rate is reduced to less than 2 L/min. Oxidative stress is accepted as a pathological mechanism. Oxidative stress is a state of oxidative damage that occurs when the critical balance between free radical production and antioxidant defense systems is disrupted. Oxidative stress is beneficial in certain physiological conditions. For example, it can strengthen biological defense mechanisms during appropriate physical exercise and ischemia. However, its benefits are limited to these specific situations, and in many other cases, high levels of oxidative stress cause cell death and, thus, cell and tissue damage through necrotic or apoptotic mechanisms. If damage continues at the cell and tissue level, it causes various organ damage and disease onset and progression. In our study, the amount of inspired oxygen is expected to be low due to keeping the gas supplied to the system low in low-flow anesthesia applications. Accordingly, the oxidative stress will be less. Therefore, this study will investigate whether low-flow anesthesia positively contributes to the total oxidant/antioxidant balance.

**Keywords:** General anesthesia, low flow anesthesia, oxidative stress

## **Introduction**

It is reported that the use of high-flow anesthesia in operating room practice is still over 80%. Low-flow anesthesia is associated with a less inflammatory response in the postoperative period than high-flow anesthesia. In addition, the low-flow anesthesia technique maintains the temperature and humidity of the respiratory system with less effect on mucociliary clearance. It preserves tracheobronchial physiology better than high-flow anesthesia. This technique also reduces the amount of waste gases released into the environment and atmospheric pollution, as well as health risks for operating room personnel, and better preserves the ecological balance. One of the most essential advantages of using low current is cost reduction.

Many risk factors can cause oxidative stress, including alcohol, drugs, environmental pollutants, intense exercise, inflammation, and sepsis. Biological targets most exposed to oxidative damage include enzymes, cell membranes, and DNA. Oxygen radicals have been implicated as an essential cause of mechanisms that can lead to the rapid degradation of proteins. Free radical-induced changes in proteins increase the degradation of enzymes. Oxidative damage to protein products can affect the activity of enzymes, receptors, and transporter proteins. Oxidatively damaged protein products may contain reactive groups that

can damage the cell membrane and many cellular functions. Peroxidation of lipids occurs when biological membranes react with unsaturated fatty acids and proceed by radical chain reaction. Oxidative events cause changes in the physical-chemical properties of membranes and thus alter fluidity and permeability, with membranes disintegrating with swelling of intracellular organelles. DNA and RNA are sensitive to oxidative damage. DNA is thought to be the main target, especially in aging and cancer. Oxidative nucleotides such as glycol, thymidine glycol, and 8-hydroxy-2- deoxyguanosine have increased during oxidative damage to DNA by UV radiation or free radical damage. Mitochondrial DNA has been reported to be more susceptible to oxidative damage in many diseases, including cancer.

In our study, two groups will be formed: low flow group and high flow group. Vitamin D, albumin, CRP, TAS, and TOS values will be checked from all patients before and during the operation. During the operation, 1 L/min fresh gas flow will be given to the low-flow group, 4 L/min fresh gas flow will be given to the high-flow group, and the processed EEG values of all patients will be monitored, and the same depth of anesthesia will be ensured. Albumin, CRP, TAS, and TOS values from the postoperative blood samples of the patients taken to the ward after the operation will be rechecked, and these values will be compared with the previous values.

Our study will compare the changes in total oxidant and total antioxidant systems in general anesthesia methods applied with 1 lt/min and 4 lt/min flows. Studies show patient-based advantages of low-flow anesthesia, such as respiratory functions and inflammatory response in the postoperative period. However, very few studies show its effects on oxidative stress, and a comprehensive study evaluating total oxidant/antioxidant systems was not found in our literature review. Therefore, our study will contribute to the literature.

## **Material and Methods**

### *Inclusion criteria:*

Patients older than 18 years and younger than 60 years to be operated under general anesthesia

Patients in the I and II risk groups, according to the American Society of Anesthesiologists (ASA) classification

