### *Exclusion criteria:*

ASA III and above patients,

Patients for whom an Intensive Care Unit (ICU) indication is foreseen

Chronic obstructive pulmonary disease,

A personal or family history of malignant hyperthermia,

Morbid obesity,

Alcohol or drug addiction,

History of liver or kidney disease,

With coronary artery disease or heart failure,

Significant anemia or hemoglobinopathy,

Hypotension, hypovolemia, sepsis.

After the patients who meet the specified criteria are informed about the study, volunteers who agree to participate and sign an informed consent will be included. Vitamin D, albumin, CRP, Total Antioxidant Status (TAS), and Total Oxidant Status (TOS) levels will be measured in the blood samples obtained from all volunteers' preoperative routine blood samples. After all volunteers are admitted to the operation room, they will be monitored with electrocardiography, pulse oximetry, non-invasive blood pressure, end-tidal carbon dioxide, temperature probe, and processed electroencephalogram- -bispectral index (BIS) without any medication. Baseline peak heart rate (HR), peripheral oxygen saturation (SpO2), systolic (SBP) and diastolic blood pressure (DBP), end-tidal carbon dioxide (ETCO2), body temperature, and BIS will be recorded. All measurements will be repeated and recorded at 5-minute intervals during the operation.

Volunteers will be divided into low-flow group (D) and high-flow group (Y). D group will receive 1 L/min fresh gas flow, and Y group will receive 4 L/min fresh gas flow. Processed EEG values of all patients will be monitored during the operation and ensured they are at the same depth of anesthesia. Albumin, CRP, TAS, and TOS values will be rechecked in the postoperative blood samples of the patients during and after the operation and compared with the previous values.

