#### **Statistical Analysis Plan**

The Shapiro-Wilk test will be used to check the normal distribution of the numerical data, and the kurtosis and skewness coefficients will also be examined. Variance homogeneity will be analyzed using Levene's test. Independent samples t-test, Welch test, or Mann-Whitney U test will compare the groups depending on the data distribution. Depending on the expected value rule, categorical variables will be analyzed using Pearson chi-square, Fisher's exact, or Fisher-Freeman-Halton tests. A comparison of the values measured at different periods during the operation will be performed using repeated measures ANOVA. Pearson correlation or Spearman's rho will be used in correlation analyses depending on the data distribution. Descriptive statistics will be given as mean±standard deviation or median, quartiles, and minimum-maximum values depending on the data distribution, and categorical variables will

be summarized as numbers and percentages. Statistical analyses will be performed using SPSS v.22 (IBM Corp. Released 2013. IBM SPSS Statistics for Windows, Version 22.0. Armonk, NY: IBM Corp.) package program, and the significance level will be taken as 0.05.

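### Surgery type and length are left open and the group comparisons adjust for nothing, so variation caused by the operation lowers precision

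*Combined protocol and SAP*

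**What the plan says.** **Eligibility.** The inclusion criteria are "Patients older than 18 years and younger than 60 years to be operated under general anesthesia" and "Patients in the I and II risk groups, according to the American Society of Anesthesiologists (ASA) classification". ASA class grades the patient, not the procedure. Among the exclusions, only "Patients for whom an Intensive Care Unit (ICU) indication is foreseen" bears on the operation. It probably removes some major surgery, but it sets no limit on type or length.

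**Allocation.** The text after the exclusion criteria says "Volunteers will be divided into low-flow group (D) and high-flow group (Y"). The text available to this review gives no method, ratio or strata. Part of the Methods between that section and the success criteria was not available, so it cannot be said that the plan lacks randomisation or stratification.

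**Aim.** The Introduction states: "Our study will compare the changes in total oxidant and total antioxidant systems in general anesthesia methods applied with 1 lt/min and 4 lt/min flows". Albumin and CRP are compared with their earlier values as well.

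**Analysis.** The Statistical Analysis Plan states: "Independent samples t-test, Welch test, or Mann-Whitney U test will compare the groups depending on the data distribution". For intraoperative values: "A comparison of the values measured at different periods during the operation will be performed using repeated measures ANOVA". It also lists correlation analyses. It names no covariate, stratification factor, ANCOVA or regression model, and does not mention surgery type or duration.

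**Link to the outcome.** The Introduction says: "Many risk factors can cause oxidative stress, including alcohol, drugs, environmental pollutants, intense exercise, inflammation, and sepsis".

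**The concern.** The markers respond to more than gas flow. The protocol itself counts inflammation among the causes of oxidative stress, and CRP, one of the measured markers, is an index of inflammation. A short minor procedure and a long extensive one plausibly move TAS, TOS, CRP and albumin by different amounts whatever the flow. They also differ in the minutes spent at the assigned flow, which is the exposure under study.

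With unadjusted tests, all of that variation counts as noise. The likely cost is a missed flow effect or a wide confidence interval. Comparing with preoperative values removes stable differences between patients, but not the change that the operation produces. A second possible cost arises if one group happens to receive more extensive surgery, because part of the difference may then be read as an effect of flow.

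**Working it through.** The available text gives no sample size, SD, effect size or power, so there is no planned figure to reproduce. Only the 0.05 significance level comes from the SAP (two-sided assumed). All other inputs are assumptions, shown as ranges.

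**1. Precision.** Let R² be the share of outcome variance explained by surgical category and planned duration. Adjustment multiplies the residual SD by √(1 − R²). A comparison with 80% power unadjusted has a standardised signal of 1.96 + 0.84 = 2.80, so adjusted power = Φ(2.80/√(1 − R²) − 1.96).

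| R² (assumed) | 2.80/√(1 − R²) | Adjusted power | Unadjusted variance relative to adjusted, 1/(1 − R²) |
|---|---|---|---|
| 0.10 | 2.95 | 84% | 1.11 |
| 0.20 | 3.13 | 88% | 1.25 |
| 0.30 | 3.35 | 92% | 1.43 |
| 0.40 | 3.62 | 95% | 1.67 |

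For scale, a standardised difference of 0.5 needs 63 per group unadjusted, and 57, 51 or 44 per group at R² of 0.1, 0.2 or 0.3.

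**2. Chance imbalance under simple randomisation.** Assume 30 or 40 per group and a surgical category present in half the patients. The probability that the groups differ by 20 percentage points or more, from two independent binomial counts, is about 16% (n = 30) and 9% (n = 40).

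**3. False-positive rate given such an imbalance.** Fix the category at 60% in one group and 40% in the other, with a 1 SD shift in the marker and no flow effect. The bias is 0.2 × 1 = 0.2. The variance that the t-test sees is v_g = v_w + 0.24 × n/(n − 1), where 0.24 = 0.6 × 0.4 and v_w is the variance within a category. If the SD is the within-category SD, v_w = 1. If it is the total SD, v_w = 1 − 0.25 = 0.75. With the imbalance fixed, the test statistic has approximate mean m = 0.2/√(2v_g/n) and SD s = √(v_w/v_g). The rejection rate is then 1 − Φ((1.96 − m)/s) + Φ((−1.96 − m)/s).

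| n per group | v_w | m | s | Formula | Simulated t-test (200,000 runs) |
|---|---|---|---|---|---|
| 30 | 1 | 0.69 | 0.90 | 8.0% | 7.9% |
| 30 | 0.75 | 0.78 | 0.87 | 8.7% | 8.5% |
| 40 | 1 | 0.80 | 0.90 | 9.9% | 9.8% |
| 40 | 0.75 | 0.90 | 0.87 | 11.1% | 11.0% |

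**4. False-positive rate over all allocations.** When the category falls at random in both groups, the same unadjusted t-test rejects in 5.0% of simulated trials at both sample sizes.

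**The case against.** The strongest reply is that an unadjusted comparison of randomised groups is valid and that covariate adjustment is a choice about efficiency. That stands, and step 4 of the working supports it. It does not answer the loss of precision, which is present whether or not allocation is randomised.

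A reader might infer that the flow effect is confounded by surgery. The documents do not support that. The available text says only that volunteers are divided, and the part not seen may describe randomisation or stratification. Confounding in the systematic sense would need an allocation related to the planned operation.

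A reader might also put the false-positive rate at 12% to 15% for a 20-point imbalance. That comes from 0.2 × √(n/2), which is 0.77 at n = 30 and 0.89 at n = 40, set against a unit-SD test statistic. It is too high. Once the imbalance is fixed, the variance due to the category is no longer sampling error, yet it still sits in the denominator of the t-test. Even the corrected rate applies only to trials with that imbalance.

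It can fairly be said that nothing in the documents fixes R² for TAS or TOS. At 10% to 20% the gain is only 4 to 8 points of power, and the foreseen-ICU exclusion together with ASA I–II may narrow the range of operations. This limits the size of the point, but the reason for adjusting remains.

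**Conclusion.** The point holds as one about precision. Eligibility leaves the type and length of surgery open apart from the foreseen-ICU exclusion, and no planned comparison adjusts for either of them or, as a covariate, for the preoperative marker value already collected. Under an assumed R² of 10% to 40%, adjustment is worth about 4 to 15 points of power on an 80% base. The documents do not show which end applies.

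Bias is a conditional and smaller matter. With randomised allocation, the type I error is 5% overall. It rises to about 8–9% (n = 30) or 10–11% (n = 40) only in trials with the 20-point imbalance and 1 SD shift described. If allocation proves not to be randomised, the risk of bias would have to be judged again. This is a worthwhile, inexpensive improvement and does not make the planned tests invalid.

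**What to change.** Keep eligibility as it is.

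- **Data collection.** Record surgical category (a short sponsor-defined list) and planned duration before allocation.
- **SAP.** Make the primary between-group comparison of postoperative TAS and TOS, and of CRP and albumin, an ANCOVA with the preoperative marker value, surgical category and planned duration as covariates. Report the adjusted difference with its confidence interval. Keep the current unadjusted tests as supportive analyses.
- **Exposure.** Report actual minutes at the assigned flow by group. Because they arise after allocation, use them only in a supportive analysis.
- **Allocation.** If allocation is not already stratified and enrolment is not complete, surgical category may also serve as a stratum.
- **If enrolment is complete.** Surgical category could be taken from operative records and fixed as a covariate before the marker data are analysed.

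The cost is two preoperative fields and a revised SAP paragraph. The downside is that the categories must be few so that cells do not become sparse.

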### *Exclusion criteria:*

ASA III and above patients,

Patients for whom an Intensive Care Unit (ICU) indication is foreseen

Chronic obstructive pulmonary disease,

A personal or family history of malignant hyperthermia,

Morbid obesity,

Alcohol or drug addiction,

History of liver or kidney disease,

With coronary artery disease or heart failure,

Significant anemia or hemoglobinopathy,

Hypotension, hypovolemia, sepsis.

After the patients who meet the specified criteria are informed about the study, volunteers who agree to participate and sign an informed consent will be included. Vitamin D, albumin, CRP, Total Antioxidant Status (TAS), and Total Oxidant Status (TOS) levels will be measured in the blood samples obtained from all volunteers' preoperative routine blood samples. After all volunteers are admitted to the operation room, they will be monitored with electrocardiography, pulse oximetry, non-invasive blood pressure, end-tidal carbon dioxide, temperature probe, and processed electroencephalogram- -bispectral index (BIS) without any medication. Baseline peak heart rate (HR), peripheral oxygen saturation (SpO2), systolic (SBP) and diastolic blood pressure (DBP), end-tidal carbon dioxide (ETCO2), body temperature, and BIS will be recorded. All measurements will be repeated and recorded at 5-minute intervals during the operation.

Volunteers will be divided into low-flow group (D) and high-flow group (Y). D group will receive 1 L/min fresh gas flow, and Y group will receive 4 L/min fresh gas flow. Processed EEG values of all patients will be monitored during the operation and ensured they are at the same depth of anesthesia. Albumin, CRP, TAS, and TOS values will be rechecked in the postoperative blood samples of the patients during and after the operation and compared with the previous values.

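### Preoperative CRP, TAS and TOS are measured in every volunteer, but the flow comparison is unadjusted, so variation from non-septic inflammation costs precision that could be partly recovered

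*Combined protocol and SAP*

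**What the plan says.** The Introduction states: "Many risk factors can cause oxidative stress, including alcohol, drugs, environmental pollutants, intense exercise, inflammation, and sepsis". Inflammation and sepsis are separate items in that list.

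The inclusion criteria admit "Patients older than 18 years and younger than 60 years to be operated under general anesthesia" and "Patients in the I and II risk groups, according to the American Society of Anesthesiologists (ASA) classification". They do not restrict the indication for surgery. The exclusion criteria cover two of the other listed causes through "Alcohol or drug addiction", and they end with "Hypotension, hypovolemia, sepsis". They have no entry for non-septic infection, inflammatory disease or raised CRP.

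On sampling, the text under the exclusion criteria says that, before surgery, "Vitamin D, albumin, CRP, Total Antioxidant Status (TAS), and Total Oxidant Status (TOS) levels will be measured" in all volunteers. The objective in the Introduction is: "Our study will compare the changes in total oxidant and total antioxidant systems in general anesthesia methods applied with 1 lt/min and 4 lt/min flows".

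The Statistical Analysis Plan compares the groups by t, Welch or Mann-Whitney tests, chosen by distribution. Repeated-measures ANOVA is used for values taken at different times during the operation, and correlations are mentioned in general terms. No covariate is named for any comparison.

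**The concern.** A patient operated on for a localised inflammatory condition may start with abnormal CRP and TOS. Both can then move as the disease evolves or its source is removed. A change score removes a constant offset between patients, but not a marker that is moving for reasons of its own. That movement adds spread to the TAS and TOS changes that has nothing to do with gas flow.

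The plan already collects the baseline information that could explain part of this spread, and the stated tests do not use it. At stake is the trial's ability to detect a flow effect of a given size.

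**Working it through.** **Inputs.** The readable documents give no sample size, SD, effect size or power, so there is no stated figure to reproduce. All inputs below are assumptions:

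- *p*, the share of enrolled patients with active inflammation: 10% to 20%.
- *s*, the shift in their mean TAS or TOS change, in SDs of the other patients' change: 0.5 to 2.
- Two-sided alpha of 0.05 (the plan gives 0.05 without sidedness).
- For the power column, a true flow effect of 0.5 SD, for which 63 per arm gives 80% power when no patient is inflamed.

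**Step 1: variance with random allocation.** Variance factor = 1 + s²p(1−p). The standard error grows by its square root.

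| s | p | Variance factor | SE increase | Power at 63 per arm | Per arm for 80% |
|---|---|---|---|---|---|
| 0.5 | 10% | 1 + 0.25×0.09 = 1.02 | 1% | 79% | 65 |
| 0.5 | 20% | 1 + 0.25×0.16 = 1.04 | 2% | 79% | 66 |
| 1 | 10% | 1 + 1×0.09 = 1.09 | 4% | 77% | 69 |
| 1 | 20% | 1 + 1×0.16 = 1.16 | 8% | 74% | 73 |
| 2 | 10% | 1 + 4×0.09 = 1.36 | 17% | 67% | 86 |
| 2 | 20% | 1 + 4×0.16 = 1.64 | 28% | 59% | 103 |

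The shift dominates because it enters squared. At 0.5 SD the loss is negligible.

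**Step 2: chance imbalance is the same quantity.** Take 30 per arm, p = 15% and s = 2 (assumed).

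- SE of the group difference without the subgroup: √(2/30) = 0.258 SD.
- SD of the between-arm difference in prevalence: √(2×0.15×0.85/30) = 0.092. Times the 2 SD shift, this is 0.184 SD.
- Combined: √(0.258² + 0.184²) = 0.317 SD.
- From the variance factor, 1 + 4×0.15×0.85 = 1.51: √(2×1.51/30) = 0.317 SD.

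The two routes agree. The imbalance is a component of the inflated standard error, and adding it as a second harm would count it twice.

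**Step 3: upper limit on what adjustment recovers.** The subgroup accounts for s²p(1−p) / [1 + s²p(1−p)] of the outcome variance: 0.0225/1.0225 = 2% at the low end and 0.64/1.64 = 39% at the high end. A CRP covariate recovers all of this only if it separates the inflamed patients perfectly. Otherwise it recovers less.

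**The case against.** **Inflammation was not meant to be excluded.** The list of causes is background and not a rationale for eligibility. Environmental pollutants and intense exercise are on the same list and are not excluded either. This stands: a reader might infer that the eligibility criteria contradict the Introduction, but the documents do not support that.

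**Few such patients may enrol.** Routine preoperative samples and planned operation dates suggest scheduled surgery. Exclusion of ASA III and above, foreseen intensive care, COPD, and liver or kidney disease removes some inflamed patients. This also stands as far as it goes. No criterion limits urgency or indication, but the assumed 10% to 20% cannot be derived from the text.

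**Disease course could produce a false flow effect.** A reader might go further and infer this. With 20% inflamed and 30 per arm (both assumed), a chance imbalance of at least 10 percentage points arises in about 42% of randomised trials. However, Step 2 shows that the standard error already reflects such imbalances, so the false-positive rate of the planned tests stays near 5%. Higher rates need a fixed imbalance. With 50 per arm, for example, the rate is 7.6% for a 1 SD shift with 10% against 20% inflamed, and 35% for a 2 SD shift with 10% against 30%. Nothing in the documents shows an imbalance of that kind.

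**Adjustment may gain little.** The documents do not show how closely CRP tracks the TAS or TOS change. This stands and limits the claim.

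**Conclusion.** The point holds as a low-severity, optional improvement in precision. Patients with non-septic inflammation can enter, the relevant baseline values are collected, and the readable analysis plan leaves them out of the flow comparison. Under the assumed ranges, the standard error is about 1% to 28% larger than it would be without that subgroup. The upper end rests on a 2 SD shift for which the documents offer no support.

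The conclusion that precision is lost without bias depends on random allocation. The readable text says only that volunteers are divided into the two groups. The text between the exclusion criteria and the Success Criteria section was not available, so allocation and any use of CRP should be checked there first.

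A reader might also infer that a CRP-based exclusion is needed. The documents do not support that step. It would narrow the population, and it would require the CRP result before enrolment, whereas the plan includes consenting volunteers and describes the measurement afterwards.

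**What to change.** In the Statistical Analysis Plan, prespecify the TAS and TOS flow comparison as an ANCOVA. The outcome is the postoperative value and the factor is flow group. The covariates are the preoperative value of the same marker and log preoperative CRP. With the preoperative value in the model, the group effect is the same whether the outcome is the postoperative value or the change, so the stated objective is kept. Use only the preoperative CRP, because later CRP values could themselves be affected by flow. State how CRP results below the assay's reporting limit enter the logarithm.

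Add one sensitivity analysis that repeats the comparison without patients whose preoperative CRP is above the laboratory's normal limit. Leave the eligibility criteria unchanged on this point.

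The cost is one degree of freedom per covariate. At an assumed 30 per arm, the residual degrees of freedom fall from 58 to 56. No additional blood test is needed, and the change can still be made after enrolment has begun, provided it is fixed before the outcome data are examined.
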